Finally, in order to better investigate if reducing these diagnostic errors leads to improved patient outcomes, we will ask practices one time during the 2 year collaborative to identify the time between when the appropriate information to diagnose the patient was available and when the actual diagnosis was conveyed to the family. Practices who have intervened on a given error will track 50 patient charts with one of the following metrics: 1) time between positive mental health screen and diagnosis of depression or depression diagnosis ruled out, 2) the number of days between blood pressure elevation in the medical record and notification of the family, or 3) time between abnormal laboratory result received and notification of family. Additionally, we will ask practices to evaluate 50 patients with a delayed diagnosis of actionable laboratory results 6 months after the diagnostic opportunity to evaluate for emergency department visits, clinic visits, ultimate diagnosis, clinical worsening in laboratory values and other patient morbidities. Similarly, we will ask intervention practices to evaluate 50 patients whose diagnostic instrument of the PHQ-9M was positive 6 months after the diagnostic opportunity to evaluate how many were ultimately diagnosed with depression, attended initial mental health appointments and were referred to mental health or were diagnosed directly by the pediatrician.

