The missed diagnosis of adolescent depression primary outcome measure is defined as the incidence of depression in adolescents  $\geq$ 11 years old compared in intervention versus control practices. This outcome measure was chosen because prior research suggested up to 75% of adolescent cases are missed by primary providers, allowing incidence to serve as a proxy for missed diagnoses. The research team strongly considered using documented depressive symptoms (e.g. poor school performance, interrupted sleep patterns, increased disruptive behaviors, etc.) without appropriate provider identification or referral to mental health evaluation as the missed diagnosis of adolescent depression primary outcome. This metric was not chosen because preliminary data suggested the number of adolescents with symptoms suggestive of depression documented prior to a mental health referral was extremely small. This finding echoes research that pediatricians' use of adolescent and parental chief complaints to identify depressive risk factors consistently under identifies adolescent depression. The process measure for this diagnostic error will be the percent of adolescents screened for depression, a practice recommended for all adolescents by the USPSTF, and feasible and acceptable to primary care pediatricians.

 Table 2: Outcome and Process Measures, and Evidence-Based Tools for Diagnostic Error

 Reduction

Primary Outcome Measure	Process Measures	Evidence-Based Tools
Number of Adolescents Diagnosed with	1 Number of adolescents	1 Patient screening in the
Depression per 100 Adolescent Visits	screened for depression	waiting room
Patients >11 years old with documentation of	with the $PHO_9-M$ per total	2 Triage purse scoring and
major depression or subsyndromal depression	number of adolescents	flagging to facilitate
diagnoses	seen per month	provider recognition
Flevated Blood Pressure Not Recognized by	1 Number of patients >3	1 Triage nurse or FHR
Providers per 100 Elevated Blood Pressures	vears old with blood	flagging of elevated
Measured	pressure checked at triage	blood pressures to
Systolic or Diastolic Blood Pressure > 90 th	per total number of	facilitate provider
percentile for age, gender and height or $>120/80$	patients >3 years old seen	recognition
in >3 years old patients without history of		2. Family notification of
hypertension and none of: 1) provider repeated		elevated blood pressure

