blood pressure, 2) clinic note mentions elevated		at triage
blood pressure/hypertension 3) plan included		
recheck or evaluation of blood pressure, or 4)		
ordering laboratory or other studies to evaluate		
elevated blood pressure		
Delayed Actions on Laboratory Results per	1. Percent of providers with	1. Weekly nurse review of
100 Abnormal Laboratory Results Received 	unread or	all abnormal laboratory
No documented action step for first positive after	unacknowledged	results
30 days:	laboratory results in their	2. Standardized protocols
1. Hgb similar and MCV similar 2 year old $\rightarrow$	EHR inbox for greater than	for handling laboratory
documentation of beginning iron, sending	72 hours	results
Iron studies or family conversation		3. Standing orders for
2. Lead >5 > documentation of family		laboratory results action
conversation on lead remediation or plan to		steps to be completed by
No documented action atom for first positive after		nuise with appropriate
		provider oversight
1 Dositive Conorrhea Chlamydia Synhilis or		
HIV test documentation of antibiotics		
heave or referral to HIV specialist		
2 Positive group A streptococcal throat culture		
with negative rapid group A streptococcal		

	test→documentation of antibiotics begur family conversation	ı or
3.	TSH $\leq$ 0.5 or $\geq$ 4.5 in $\geq$ 1 year old $\rightarrow$ plan	to
	repeat lab values or referral endocrinologist	to

Early detection via screening represents the best opportunity to reduce missed diagnosis of adolescent depression. We will screen patients with the Patient Health Questionnaire 9-item Modified for Adolescents (PHQ-9-M), as it is a validated and highly specific tool (94.7%). Building on work done by [name], a member of the Project Expert Group and others, we will use coaching and learning sessions to ensure appropriate follow-up for identified mental health concerns are in place before practices begin universal screening. The evidence-based tools utilized by the collaborative to improve diagnosis of adolescent depression include patient screening in the waiting room, followed by nurse scoring and flagging. This methodology increased adolescent screening rates to 80-84% in QI interventions at CHAM and in 6 non-affiliated sites, and is a necessary first step to adolescent depression diagnosis.

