The final set of data will be aggregate data of patients one time during the 2 year collaborative to identify the time between when the appropriate information to diagnose the patient was available and when the actual diagnosis was conveyed to the family. Practices who have intervened on a given error will track 50 patient charts with one of the following metrics: 1) time between positive mental health screen and diagnosis of depression or depression diagnosis ruled out, 2) the number of days between blood pressure elevation in the medical record and notification of the family, or 3) time between abnormal laboratory result received and notification of family, we will ask practices to identify, in the same 50 patients with

a delayed diagnosis of actionable laboratory results 6 months after the diagnostic opportunity to evaluate for emergency department visits, clinic visits, ultimate diagnosis, clinical worsening in laboratory values and other patient morbidities. Similarly, we will ask intervention practices to evaluate 50 patients whose diagnostic instrument of the PHQ-9M was positive 6 months after the diagnostic opportunity to evaluate how many were ultimately diagnosed with depression, attended initial mental health appointments and were referred to mental health or were diagnosed directly by the pediatrician.. This final set of data will be collected only once between 12-18 months after the intervention period begins.

For research and publications that may result from this work, all data will be reported in aggregate, and individual and practice data will not be identifiable. If practice data is presented, each practice will receive an ID number in the report. Potential publications may include a conceptual model of key barriers and potentially useful strategies that emerged from this project. No patients or practice staff will be identified in any report or publication about this study. Practice names will only be used in the acknowledgement section of any potential publication.

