Power Analysis: Assuming a two sided alpha level of 0.05 and >80% power, we calculated the effect size we could detect for each of the 3 diagnostic error primary outcome measures, comparing the 10-20 intervention practices, given the stepped wedge design, to the 10-20 control practices using the above models, and the QIC methodology and preliminary data. 1) Missed diagnosis of depression: If each practice screens 17 adolescent charts a month, we are able to detect an effect size of 2.4% or a reduction in the diagnostic error rate as small as 33% (intra-class correlation coefficient (ICC)=0.005). 2) Missed diagnosis of pediatric elevated blood pressure: If each practice screens 10 patient charts with elevated blood pressure a month, we are able to detect an effect size of 12% or a reduction in the diagnostic error rate as small as 13% (ICC=0.1). 3) Delayed diagnosis of actionable laboratory results: If each practice collects 10 patient charts with abnormal laboratory values a month, we are able to detect an effect size of 12% or a reduction in the diagnostic error rate as small as 13% (ICC=0.1). Although we are testing three outcomes, we do not correct the alpha level for multiple testing since the study subjects will most likely be different across the three outcome comparisons.

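### The depression primary outcome scores every added charted diagnosis as a missed case found, so incorrect diagnoses prompted by screening would inflate the apparent benefit

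*Combined protocol and SAP*

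**What the plan says.** All references are to the combined protocol and SAP.

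- **Outcome.** Under *Target Diagnostic Error Outcome Measures* (section 2), the depression outcome is the incidence of depression in adolescents aged 11 or over, compared between intervention and control practices. The justification is that up to three quarters of cases are missed, "allowing incidence to serve as a proxy for missed diagnoses". Table 2 and section 7 put both major and subsyndromal depression in the numerator and adolescent visits in the denominator.
- **Ascertainment.** *QIC Data Collection and Standardization* counts a case when the diagnosis appears in the problem list or the assessment part of a visit note. No confirmation is required.
- **Model.** *Statistical Models* (section 7) describes the individual outcome as missed/delayed or not. For depression, what the chart shows is diagnosed or not.
- **Intervention.** The text after Table 2 adopts the PHQ-9-M "as it is a validated and highly specific tool (94.7" per cent), with nurse scoring and flagging, and cites coverage of 80-84% in earlier work. Under *Methods*, practices get feedback and coaching only on the error they are currently intervening on.
- **Follow-up of positives.** Outcomes after a positive depression screen are a secondary objective. Practices record once, in 50 charts, the "time between positive mental health screen and diagnosis of depression or depression diagnosis ruled out". Intervention practices also review 50 PHQ-9-M positives at 6 months "to evaluate how many were ultimately diagnosed with depression".
- **Power.** "If each practice screens 17 adolescent charts a month, we are able to detect an effect size of 2.4" percentage points, or "a reduction in the diagnostic error rate as small as 33% (intra-class correlation coefficient (ICC)=0.005".

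**The concern.** The Background section counts an incorrect diagnosis as a diagnostic error, alongside a missed or a delayed one. The depression outcome can only improve when diagnoses are added, so an incorrect diagnosis is scored as an error prevented.

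The other two outcomes are less exposed. Their denominators are elevated blood pressures and abnormal laboratory results, so labelling a healthy child cannot improve them. The depression denominator is all adolescent visits, so over-labelling can.

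The bias has a direction. The collaborative brings screening and flagging to the practices intervening on depression, and any false positives come with it. Randomization does not remove a measurement artefact that the intervention itself causes. At stake is the wording of the main claim: part of a reported fall in missed diagnoses could be a rise in incorrect ones.

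**Working it through.** **1. Inputs**

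| Quantity | Value | Source |
|---|---|---|
| Prevalence of depression | about 10% | Background |
| Share of cases missed | about 75% | Background |
| Specificity of PHQ-9-M | 94.7% | text after Table 2 |
| Screening coverage | 80-84% | text after Table 2 |
| Hypothesised reduction | 40% | Hypothesis 1 |
| Detectable effect | 2.4 points, or 33%; ICC 0.005 | Power Analysis |
| Practices per arm | 10-20 | Power Analysis |
| Share of false-positive screens charted as a diagnosis | 10-50% | assumption; not in the documents |

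**2. The plan's detectable effect.** The stated basis is "Assuming a two sided alpha level of 0.05 and >80% power", "comparing the 10-20 intervention practices, given the stepped wedge design, to the 10-20 control practices". The base rate is not given; 2.4 / 0.33 implies 7.3 missed per 100, close to 10 x 0.75 = 7.5. With 20 practices per arm, 8 months and 17 charts a month:

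- charts per practice = 17 x 8 = 136; charts per arm = 20 x 136 = 2,720
- design effect = 1 + (136 - 1) x 0.005 = 1.675
- effective n per arm = 2,720 / 1.675 = 1,624

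A two-proportion test then has power 0.82 for 7.3 to 4.9 and 0.80 for 7.5 to 5.1, so 2.4 points reproduces. On the diagnosed scale (2.5 rising to 4.9) it also reproduces with 12 practices x 8 months (power 0.80) or 10 practices x 12 months (0.82). It does not with 10 practices x 8 months, where the detectable difference is 2.7 points on the diagnosed scale and 3.2-3.3 on the missed scale. I use 2.4 as the yardstick. The Hypothesis 1 effect is 0.40 x 7.5 = 3.0 per 100.

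**3. False-positive screens per 100 adolescents** = 100 x (1 - prevalence) x (1 - specificity) x coverage

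- 80% coverage: 100 x 0.90 x 0.053 x 0.80 = 3.8
- 84% coverage: 100 x 0.90 x 0.053 x 0.84 = 4.0

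These are screens, not outcome events.

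**4. Added events if a share of them is charted** (no screening in control practices, one visit per adolescent)

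- 10%: 0.10 x 3.8 to 4.0 = about 0.4, or 0.4 / 2.4 = 17% of the detectable effect
- 25%: about 1.0, or 40%
- 50%: 1.9-2.0, or up to 83%

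**5. What moves the result**

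- *Control practices also screen.* The coverage difference replaces coverage in step 3. At an assumed 20% control coverage, the excess is 4.77 x (0.60 to 0.64) = 2.9-3.1 screens per 100, so 0.3-1.5 added events. At 40%, it is 4.77 x (0.40 to 0.44) = 1.9-2.1, so 0.2-1.0.
- *Specificity.* At an assumed 98%, the yield at 80% coverage is 100 x 0.90 x 0.02 x 0.80 = 1.4, so 0.1-0.7 added. At an assumed 90%, it is 7.2, so 0.7-3.6 added.
- *Target condition.* The documents do not say which condition or cut-off the 94.7% refers to. If it is major depression only, some of these positives are true subsyndromal cases, which the outcome rightly counts.

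**6. Share needed to reach 2.4 with no true case found:** 2.4 / 4.0 = 60% to 2.4 / 3.8 = 63%.

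**The case against.** The strongest reply is that a positive screen is not an outcome event. The event is a clinician's charted diagnosis; screening is a separate process measure. The plan also wants follow-up of mental health concerns in place before universal screening begins, and it says that a symptom-based measure of missed diagnosis was considered and dropped because preliminary counts were extremely small. Outcomes after positive screens are already a secondary objective. All of this stands, and it makes the charted share of false positives unknown. It does not close the gap: the plan has no rule for a diagnosis that proves wrong. The rule-out timing and the 6-month review are collected once, the latter in intervention practices only, and neither enters the primary outcome.

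A reader might go further and infer that false positives could by themselves produce the effect the trial looks for, since 3.8-4.0 exceeds both 2.4 and 3.0. The documents do not support that. It would need 60-63% of false-positive screens to be charted, no additional true case found, no screening in control practices, and a specificity that applies to subsyndromal as well as major depression. The plan gives no charted share, and it describes screening as already recommended for all adolescents. Under an assumed sensitivity of 60-90%, screening would also pick up 7.5 x (0.80 to 0.84) x (0.6 to 0.9) = 3.6-5.7 true missed cases per 100. Charting most false positives and none of these is a corner case.

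**Conclusion.** The point holds as a risk of inflation, and acting on it is a cheap improvement. The outcome cannot tell an added correct diagnosis from an added incorrect one, and the error runs in favour of the intervention. The plausible size is about 0.4-2.0 per 100 against a detectable 2.4, given 10% prevalence, 94.7% specificity, 80-84% coverage, one visit per adolescent, no screening in control practices and an assumed 10-50% charted share. Background screening in control practices, or true subsyndromal cases among the positives, would make it smaller. This is a possibility and not a prediction. It limits how the result may be described; it does not make the comparison of recorded diagnoses invalid.

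**What to change.** 1. **Coding rule.** In the chart tool, score no event when the entry is only a PHQ-9-M result or flag, or when the diagnosis is already ruled out at review. The first half largely makes the existing definition explicit. The second catches only early rule-outs, because monthly charts come from the prior month.
2. **Separate fields.** Record major and subsyndromal depression separately, and pre-specify the intervention-control comparison on major depression alone as a sensitivity analysis.
3. **Use the planned 6-month review.** Among the 50 PHQ-9-M positives, report for those who received a charted depression diagnosis the share retained and the share later ruled out. This is descriptive context only: there is no reference standard and no matching control review.
4. **Wording.** Report the primary result as a difference in recorded depression diagnoses. Describe it as fewer missed diagnoses only with the proxy assumption stated and items 2 and 3 shown beside it.

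Do not multiply the primary difference by the confirmed share of all screen positives. That share has screens as its denominator, while the primary difference counts diagnoses. If clinicians ruled out every false positive before charting, a gain of 3.0 would be wholly true. Yet with a true share of 49-59% among positives (3.6 / 7.4 to 5.4 / 9.2, at 80% coverage and 60-90% assumed sensitivity), scaling would report only 1.5-1.8. A fixed positive multiplier also leaves the test statistic unchanged, so it cannot decide whether a difference remains.

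**Cost.** One extra field on charts already reviewed, a slightly lower event count, and low power for the major-only analysis. The primary endpoint stays a count of charted diagnoses, and the chart quota does not change.

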An initial orientation session will teach all practices to identify each of these 3 diagnostic errors via chart review, collect data and reliably enter it into the QuIIN IT system, QIDA. The QIDA system has been used by prior QuIIN projects, is web-based and HIPAA compliant, and QuIIN will take responsibility for data security. QuIIN's project manager has experiencing ensuring accurate and timely data submission for primary care pediatric practices from prior

Practice			
Baseline	QIC Intervention Period		
(One Time Data Collection)	(Monthly Data Collection)		
Missed Adolescent Depression			
50 > 11 year old patient charts who	17 11 year old patient charts who		
visited clinic in prior 6 months.	visited clinic in prior month. Chart		
Chart screened for depression	screened for depression		
diagnosis.	diagnosis.		
Missed Elevated Blood Pressure			
50 2 year old patient charts with	10 2 year old patient charts with		
elevated blood pressure recorded	elevated blood pressure recorded		
at triage. Chart screened for	at triage. Chart screened for		
provider recognition.	provider recognition.		
Delayed Diagnosis of Actionable			
Laboratory Results			
50 patient charts with abnormal	10 patient charts with abnormal		
laboratory results as defined	laboratory results as defined		
above. Chart screened for	above. Chart screened for		
appropriate action within time	appropriate action within time		
guidelines defined above.	guidelines defined above.		
*All charts screened will have the following demographic data recorded: age			

Table 3: QIC Primary Outcome Data Collection for Each

\*All charts screened will have the following demographic data recorded: age, gender and insurance status.

QuIIN QICs.

Practices will collect the primary outcome data by employing EHR based record paper-based review or dependina methods on abilities and interest of local Developing EHRs. data collection tools for both EHR and paper based practices allows for maximum generalizability of lessons learned from this collaborative. These tools will ensure standardized data collection bv disparate were practices and pilot tested with two QuIIN practices. All data collection tools will be pilot tested on paper and beta tested by a

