minimum of 2 Expert Group members (always including the QI Advisor). As described below, data will be checked for outliers or abnormal values and feedback given to practices to ensure consistency across practices. Additional data on providers' abilities to recognize abnormal results, either in mental health, blood pressure or laboratory values, will also be collected as this is an important first step in the diagnostic process. These data are described further in the Data collection section below. QIC leadership will use QIDA entered data to disseminate monthly feedback reports with full transparency and QIC benchmarking to intervention practices. Consented core QI team members from each practice will be able to access their team's data. All practices will report demographic data annually, including patient volume, number and training level of physician or physician assistant-level providers, number of nursing and office staff, university-affiliation, EHR availability, presence of trainees, estimated length of time providers take with patients, and prior self-reported work aiming to improve these diagnostic errors.

Table 3 summarizes the primary outcome data each practice will collect and the types of charts they will screen. Numbers of charts are based on power calculations described below and will be a convenience sample. Adolescents with depression will be identified by monthly chart reviews or EHR data summaries when this diagnosis is mentioned in the problem list or in assessment sections of visit notes. Pediatric elevated blood pressures will be identified by flagging blood pressure measurements at triage or pulling reports from EHR systems. Similar to the depression outcome, provider recognition will be identified when this diagnosis is mentioned in the problem list or in assessment sections of visit notes. Finally, abnormal lab results will be tracked by either EHR laboratory summary reports or laboratory management registry tools, such as those found in the AHRQ toolkit for improving office-based testing, and provider recognition will be identified when a diagnosis is mentioned in the problem list, in assessment

sections of visit notes or if medications are prescribed. Intervention practices will also report process outcomes (Table 2).

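### The depression outcome is read at the monthly chart review with no fixed follow-up, so later diagnoses after a positive screen are not counted and the H1 effect is probably attenuated by an unknown amount

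*Combined protocol and SAP*

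**What the plan says.** Under QIC Data Collection and Standardization, the rule for the depression outcome is: "Adolescents with depression will be identified by monthly chart reviews or EHR data summaries when this diagnosis is mentioned in the problem list", or in the assessment part of a visit note. Table 3 sets the monthly sample at 17 adolescents and defines it by a recent visit ("visited clinic in prior month. Chart" and so on). No later re-review is described, and referral does not count. Under Target Diagnostic Error Outcome Measures, recorded incidence is the stand-in for missed diagnoses. Table 2 counts both major and subsyndromal depression.

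The same document expects a delay between screen and diagnosis. It plans a one-time collection of the time from positive screen to diagnosis or rule-out. It also plans a look at 50 PHQ-9M-positive patients six months on, to "evaluate how many were ultimately diagnosed with depression, attended initial mental health appointments and were referred to mental health". Section 7 places this final data set at 12 to 18 months after the intervention starts. It comes from practices that have intervened and does not feed the primary outcome.

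The laboratory outcome, by contrast, has explicit limits of 7 or 30 days.

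The Power Analysis, "Assuming a two sided alpha level of 0.05 and >80% power", says for depression: "we are able to detect an effect size of 2.4% or a reduction in the diagnostic error rate as small as 33" per cent.

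**The concern.** The collaborative works by screening adolescents, flagging positives and arranging follow-up. Some screen-positive adolescents will get a charted diagnosis only after a further evaluation or a referral. If the chart is read before then, the record shows no depression diagnosis. Because incidence is the proxy, that chart is indistinguishable from one in which nobody noticed anything.

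Follow-up time is also uneven. A patient seen just before the review has a few days for a diagnosis to appear, and one seen at the start of the month has about four weeks.

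Universal screening belongs to the intervention, so screen-found cases still awaiting a diagnosis should arise mainly in intervention months. What is at stake is a smaller visible difference, and less power, on the first of three primary hypotheses.

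**Working it through.** **Inputs from the documents**
- Background: depression affects about 10% of adolescents and about 75% of cases are missed. Derived, not stated: 10 × 0.25 = 2.5 per 100 diagnosed and 10 × 0.75 = 7.5 per 100 missed.
- Hypothesis 1: a 40% reduction, so 0.40 × 7.5 = 3.0 points, and recorded diagnoses rise from 2.5% to 5.5%.
- Power Analysis: "If each practice screens 17 adolescent charts a month"; "intra-class correlation coefficient (ICC)=0.005"; "comparing the 10-20 intervention practices, given the stepped wedge design, to the 10-20 control practices".
- Methods: the first phase lasts 8 months, so 17 × 8 = 136 charts per practice. Statistical Models puts the primary test in the first study year; read as 12 months, that is 17 × 12 = 204 charts.

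**Formula.** For k practices per group and m charts per practice, the design effect is DE = 1 + (m − 1) × ICC and the effective n is k × m / DE. SE = √[p₁(1 − p₁)/n₁ + p₂(1 − p₂)/n₂]. Power = Φ(difference/SE − 1.96).

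**The plan's own figure.** 2.4 / 0.33 implies a missed rate of 7.3 per 100, close to the derived 7.5. With m = 204, DE = 1 + 203 × 0.005 = 2.015. At 10 v 10, effective n = 2,040 / 2.015 = 1,012 per group. For 2.5% v 4.9%, SE = 0.837 points and power is Φ(2.87 − 1.96) = 82%; the difference detectable at 80% power is 2.3 points. So 2.4 can be reproduced, but with a base rate and a period that the Power Analysis does not state. With m = 136, DE = 1.675, effective n = 812 and power at 10 v 10 is 73%.

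**Illustration of late charting.** Let f be the share of newly found cases not yet charted at the review. The documents give no value, so f is assumed. If the loss falls only on the extra cases in intervention months, the visible rate is 2.5 + 3.0 × (1 − f). With m = 136:

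| f (assumed) | Visible difference (points) | Power, 10 v 10 | Power, 20 v 20 |
|---|---|---|---|
| 0% | 3.0 | 87% | 99% |
| 10% | 2.7 | 81% | 98% |
| 30% | 2.1 | 63% | 90% |
| 50% | 1.5 | 40% | 67% |

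Worked line for f = 30% at 10 v 10: SE = √[(0.025 × 0.975 + 0.046 × 0.954)/812] = 0.917 points; 2.1 / 0.917 = 2.29; Φ(2.29 − 1.96) = 63%. With m = 204, the fall at 10 v 10 is from 93% to 72%.

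**If the late share is equal in both groups.** At f = 30% the rates become 1.75% and 3.85%. The odds ratio is 2.25 instead of 2.27, so the logistic estimate hardly moves. The absolute difference still shrinks to 2.1 points, and power is 73% at 10 v 10 and 95% at 20 v 20. With loss in the intervention group only, the odds ratio falls to 1.88.

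**Break-points.** With m = 136, the difference detectable at 80% power is 2.7 points at 10 v 10 and 1.8 points at 20 v 20. A true 3.0-point gain drops below these when f exceeds about 11% (1 − 2.66/3.0) and about 41% (1 − 1.78/3.0).

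**The case against.** The strongest reply is that the design recovers part of the loss. The outcome is a monthly cross-section of adolescents who attended, and a problem-list entry persists. A patient screened in one month and diagnosed in the next can be sampled at the follow-up visit or any later one. A subsyndromal diagnosis entered at the screening visit also counts, which is plausible when the nurse scores and flags the questionnaire before the provider sees the patient. All of this stands. The table treats f as lost in every month, so a given initial delay costs less than the table shows.

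Second, nothing in the documents shows that control cases are charted sooner. The lag is to be measured only in practices that have intervened. A larger loss in intervention months is an inference from where screening takes place, not a finding. If the late share is equal, the harm is mainly lost power.

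Third, the direction is toward no effect, so this cannot by itself produce a false claim of benefit. That also stands.

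Two stronger readings are tempting and not supported. A reader might set the 3.0-point hypothesis against the stated 2.4 points and conclude that late charting of more than 20% defeats the test. That mixes two power models: the formula used here gives about 11% or 41%, depending on the number of practices. A reader might also infer that a practice that screens and refers well would look no better than a control practice. Screening rates, charted mental health concerns (from intervention and control charts alike), time to diagnosis and six-month outcomes are all collected, so such a practice would be visible. None of these enters the primary outcome, however, so they do not answer the point.

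**Conclusion.** The measurement gap is real on the text. The depression outcome has uneven, short follow-up and no credit for referral, in a trial whose tool is screening and whose own plan expects a delay before diagnosis. It probably attenuates the Hypothesis 1 effect.

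The size is unknown. A fall from 87% to 63% (10 v 10) or from 99% to 90% (20 v 20) rests on an assumed 30% late share, loss confined to intervention months, no recovery at later visits, and base rates derived from the Background. It is an illustration, not an estimate. With many practices or a short lag the effect could be small. The change is worth making because it is cheap, not because the primary test is shown to fail.

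**What to change.** 1. Score each sampled adolescent's chart at one fixed interval after the index visit, the same in intervention and control months. Thirty days would match the longest window already used for laboratory results.
2. Count any qualifying diagnosis charted by then, without requiring reviewers to attribute it to that visit, and date the chart by the index visit.
3. Where the interval crosses a phase switch, cut it in the same way in both groups.
4. Add one field to the same review: referred for evaluation, not yet diagnosed. Prespecify a supportive analysis of diagnosed or referred. A diagnosis reached after the interval still will not count in the primary outcome, and this field is there for those cases.

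The cost is primary depression data about one month later, one more field on the tool, and some intervals shortened at a switch. No additional charts are needed.
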